A total of 43 participants were initially enrolled between May 2024 and February 2025 from the neurological rehabilitation clinic of the Physical Medicine and Rehabilitation Department at Biruni University Hospital. Following baseline evaluations and BTX-A injections, participants were randomly allocated into two groups: 22 patients in the Mirror Therapy (MT) group and 21 patients in the Sham Therapy (SHA) group. Permuted block randomization was employed to ensure balanced group sizes and reduce selection bias. The randomization sequence was generated using a computer-based random number system and was implemented by an independent researcher not involved in patient assessment or treatment. Group allocation was concealed using sealed, opaque envelopes until the point of assignment.

In the MT group, 4 participants were excluded due to irregular attendance (<75% session compliance), 2 participant withdrew their informed consent, and 1 were hospitalized for unrelated medical conditions requiring inpatient treatment. In the SHA group, 4 participants failed to adhere to the intervention frequency, and 2 were excluded because they received additional pain management therapies during the follow-up period.

Consequently, 15 participants in each group (n = 30 total) completed the full 6-month intervention and follow-up assessments and were included in the final statistical analysis. The overall participant flow, including recruitment, allocation, and attrition, is illustrated in.

The study was conducted according to the approved protocol and completed as planned without early termination. The follow-up period for each participant lasted six months after BTX-A injection, and all post-treatment evaluations were completed by March 2025.

All intervention sessions were delivered by the same licensed physical therapist specialized in neurorehabilitation, ensuring procedural consistency across both groups. Adherence to the

intervention protocol was closely monitored by weekly attendance tracking and therapist supervision to maintain treatment fidelity.

Participants were allocated as follows:

- **Experimental Group (Group I, n=15):** Received mirror therapy in addition to conventional rehabilitation.

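### The only between-group comparison uses the 30 completers of 43 randomised, with no as-randomised, missing-data or sensitivity analysis

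*Combined protocol and SAP*

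**What the plan says.** The participant-flow text under Study Design and Participants puts randomisation after baseline assessment and injection: "Following baseline evaluations and BTX-A injections, participants were randomly allocated into two groups", namely "22 patients in the Mirror Therapy (MT) group and 21 patients in the Sham Therapy (SHA) group".

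It then lists who was left out. In the mirror therapy (MT) arm, "4 participants were excluded due to irregular attendance (<75% session compliance", and "2 participant withdrew their informed consent, and 1 were hospitalized for unrelated medical conditions requiring inpatient treatment". In the sham arm, "4 participants failed to adhere to the intervention frequency, and 2 were excluded because they received additional pain management therapies during the follow-up period". The 15 remaining in each arm "completed the full 6-month intervention and follow-up assessments and were included in the final statistical analysis".

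The allocation list that follows gives n=15 for each group, although the same section has just given 22 and 21 as the numbers allocated.

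Evaluation Criteria has two outcome times only, baseline and six months. Statistical Analysis specifies the Mann-Whitney test (chi-square for categorical variables) between groups. It defines no analysis population and mentions no as-randomised analysis, missing-data method or sensitivity analysis; nor does any other section.

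**The concern.** All 13 people were left out after allocation, and ten of them because of what they did or received during treatment. Selecting the analysed groups on such events means that randomisation no longer guarantees their comparability. The result answers a question about people who adhered and finished, not about everyone assigned to mirror therapy or sham.

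The reasons also differ by arm. Consent withdrawal and hospitalisation appear only under MT, added pain treatment only under sham, and the 75% attendance threshold is stated only for MT. The list giving 15 allocated per group presents the completers as the randomised set.

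This is the trial's only between-group analysis, and nothing in the plan tests whether its conclusion would survive including the other 13.

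**Working it through.** **Participant flow** (inputs from Study Design and Participants)

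- MT: 22 − 4 − 2 − 1 = 15. Sham: 21 − 4 − 2 = 15. The plan's own 15 + 15 = 30 reproduces.
- Left out: MT 7/22 = 31.8%; sham 6/21 = 28.6%; total 13/43 = 30.2%.
- Attendance, adherence or added treatment: 4 (MT) + 6 (sham) = 10 of 13 (77%). Withdrawal or hospitalisation: 3, all MT.

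**How far the comparison could move.** Call the gap, in each arm, the completers' mean minus the mean of those left out. A completer mean differs from the as-randomised mean by (fraction left out) × (gap), so

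shift in the between-group difference = 0.318 × gap(MT) − 0.286 × gap(sham).

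The documents give no gap. I assume 0, 0.5 and 1 SD. The standard error of a 15 versus 15 difference is √(2/15) = 0.365 SD. The last column is the rejection rate of the exact two-sided Mann-Whitney test at 0.05 (reject if U ≤ 64 or U ≥ 161) when there is no true as-randomised difference, from 100,000 normal simulations per shift.

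| Assumed gap | Shift in SD (gap 0.5 / 1) | Shift in standard errors | Rejection rate |
|---|---|---|---|
| None | 0 | 0 | 4.4% |
| Same in both arms | 0.016 / 0.032 | 0.04 / 0.09 | 4.5% / 4.6% |
| MT only | 0.159 / 0.318 | 0.44 / 0.87 | 6.4% / 12.0% |
| Opposite in the two arms | 0.302 / 0.604 | 0.83 / 1.65 | 11.4% / 32.8% |

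The shift can go either way. This is a mean-scale calculation and only a rough guide for ordinal scales compared by ranks.

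**What a baseline comparison of left-out and retained people could show** (t-based approximation)

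- MT, 7 versus 15: √(1/7 + 1/15) = 0.458; × t(20) 2.086 = 0.95 SD.
- Sham, 6 versus 15: √(1/6 + 1/15) = 0.483; × t(19) 2.093 = 1.01 SD.

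Observed gaps smaller than these would not reach p < 0.05, so a non-significant result would not establish comparability.

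**Dates.** The same section says "A total of 43 participants were initially enrolled between May 2024 and February 2025", and also "The follow-up period for each participant lasted six months after BTX-A injection, and all post-treatment evaluations were completed by March 2025". Counting back six months from 31 March 2025 gives 30 September 2024. Anyone enrolled from October 2024 to February 2025 (5 of the 10 enrolment months) could not have a six-month assessment by the stated end, and all 30 completers would have to have been injected by about 30 September 2024. The three statements cannot all hold.

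**The case against.** The best defence is that harm is possible but not shown. Every exclusion is disclosed by arm and reason, total loss is close (31.8% versus 28.6%), and attendance or adherence exclusions are 4 in each arm. If those left out differed from completers in the same way in both arms, the shift would be only 0.02 to 0.03 SD. The larger figures depend on gaps that nothing in the documents supports. All of this is right, and it limits the weight of the upper rows of the range. It does not rescue the analysis: similar numbers left out do not show similar outcomes among them. Allocation concealment and blinded assessment do not help either, since they do not prevent selection after randomisation.

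Three smaller points have some force.

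- The text does not say that six-month outcomes were unobtainable for the ten removed for adherence or added treatment, so some may be exclusions from analysis rather than missing data.
- The date conflict is a separate contradiction, and resolving it would not change the analysis set. It is raised here because it bears on who could have been a completer.
- The participant-flow diagram is not in the text available. It might give more detail on the 13, but is unlikely to supply an analysis method.

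**Conclusion.** The concern holds. The sole between-group result is a completer, per-protocol type comparison that omits 13 of 43 randomised participants (30.2%), is not labelled as such, and has no analysis to test its robustness. The counts rest on the documents alone.

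The size and direction of any bias cannot be established from them. Under the assumed gaps the effect runs from none to 0.60 SD, or 1.65 standard errors of the comparison. The planned baseline Mann-Whitney comparison of the two groups is only a partial check, because it covers measured variables alone. The sponsor needs to correct this before drawing a conclusion about mirror therapy as assigned.

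**What to change.** 1. Label the 15 versus 15 result as completer or per-protocol and limit its conclusion to adherent completers. Correct the allocation list to 22 and 21 allocated, 15 and 15 completing.
2. Compare the 13 with the 30 on baseline data, by arm (11 if the two withdrawals do not permit use of data already collected). Report differences with 95% confidence intervals rather than p-values.
3. Add a tipping-point analysis, labelled post hoc if specified after the data were seen. Vary the assumed six-month outcome of the missing separately by arm and in both directions: points for FMA-UE, kilograms for grip strength, whole categories within scale limits for MAS and Brunnstrom. Report the combinations at which the conclusion changes. If the full set is too heavy for a trial of this size, start with the outcomes that carry the main conclusion.
4. If six-month outcomes exist for any of the 13 and consent permits their use, analyse them in the randomised arm whatever the attendance or co-treatment, and make this the main between-group result. For those still missing, use multiple imputation from arm, baseline score and attendance, pooling a stated measure such as the baseline-adjusted between-group difference. Leave co-treatment out of the imputation model: it is reported for only two participants, both sham. If no such outcomes exist, rely on steps 1 to 3, because imputing from arm and baseline alone would largely repeat the completer estimate.
5. Reconcile the enrolment and follow-up dates, and state how many of the 43 could have had a six-month assessment by the stated end.

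Steps 1, 2, 3 and 5 need no new outcome data; baseline assessment preceded allocation, so baseline scores should exist for all 43. Step 4 depends on outcomes not known to exist beyond the 30. The price is an estimate that may be diluted by non-adherence and that rests partly on missing-data assumptions.

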Study Design and Participants

This study was conducted as a randomized, sham-controlled, single-blind clinical trial to investigate the combined effects of Botulinum Toxin Type A (BTX-A) and Mirror Therapy (MT) on upper extremity spasticity in stroke patients. Ethical approval was obtained from the Institutional Review Biruni University Clinical Research Ethics Committee and all participants provided written informed consent prior to enrollment in accordance with the Declaration of Helsinki (2015-KAEK-80 23 50).

Participants were selected from the neurological rehabilitation clinic of the physical medicine and rehabilitation unit at Biruni University Hospital. Eligible patients were those diagnosed with unilateral ischemic stroke and scheduled to receive BTX-A injections for upper extremity spasticity management.

Inclusion criteria were as follows:

- Age \geq 18 years
- Diagnosis of unilateral ischemic stroke confirmed by neuroimaging (MRI or CT)
- At least 3 months post-stroke to ensure chronic phase status
- Routine follow-up under the care of the same clinician who determined BTX-A treatment indication based on established clinical guidelines
- Mini-Mental State Examination (MMSE) score > 24 to ensure adequate cognitive function for participation
- Fugl-Meyer Assessment (FMA) upper extremity motor score < 55 , indicating moderate to severe motor impairment
- Modified Ashworth Scale (MAS) score between 1 and 4 in the affected upper extremity, indicating presence of spasticity

Exclusion criteria:

- Prior BTX-A or other neurotoxin injections to the affected upper extremity within the last 6 months
- Severe cognitive impairment or psychiatric disorders interfering with communication or compliance
- Concurrent participation in other experimental rehabilitation or pharmacological trials

- Visual or motor deficits severe enough to prevent effective engagement with Mirror Therapy
- History of multiple strokes or bilateral brain lesions
- Presence of neuromuscular diseases affecting the unaffected upper extremity
- Stroke etiology other than ischemic (e.g., hemorrhagic stroke, traumatic brain injury)

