Following BTX-A injection, all participants in both groups underwent a standardized conventional upper extremity rehabilitation program for a duration of 6 months, with sessions conducted three times per week. The rehabilitation protocol included stretching exercises, passive and active-assisted range of motion exercises, coordination and balance training, as well as functional task-oriented activities. All sessions were conducted in a one-on-one setting by experienced physiotherapists.

Experimental Group (Group I): Mirror Therapy Application

In the experimental group, mirror therapy (MT) was administered in addition to conventional rehabilitation. The MT protocol was implemented as follows:

- Participants were seated upright with a large mirror placed in the midsagittal plane of the body, such that the reflection of the non-paretic extremity appeared to replace the paretic extremity.
- Movements were performed with the non-paretic extremity while patients observed the mirrored image, creating the visual illusion that the paretic extremity was moving.
- Mirror therapy was applied three times per week, with each session lasting 30 minutes, for a total of 60 sessions.
- Exercises included functional movement patterns such as finger flexion and extension, thumb abduction–adduction, and thumb opposition movements, as well as wrist flexion/extension, forearm pronation/supination, elbow flexion/extension, and simple grasp-and-release activities.

- The sequence of movements was progressively adapted to the participant's functional level, starting with isolated distal motions (finger and thumb exercises) and advancing toward combined and proximal joint movements (wrist and elbow). Patients were continuously encouraged to focus on the mirrored image to reinforce the visual illusion of symmetrical movement.

Control Group (Group II): Sham Intervention

The control group received a sham intervention designed to mimic the physical setup of mirror therapy but without inducing the visual illusion:

- A transparent glass panel was used in place of a mirror, and participants were asked to observe the reflection of their paretic extremity directly through the glass.
- This setup was intended to replicate the environment of MT without stimulating the motor cortex through visual feedback.
- The frequency, duration, and total number of sessions matched those of the experimental group (3 sessions/week, 30 minutes per session, 60 sessions in total).

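### Randomised participants were removed for reasons not set out in advance and reported differently by arm, including added pain treatment in sham only, so like selection of the analysed sets cannot be verified

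*Combined protocol and SAP*

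**What the plan says.** All the relevant text is in the combined protocol and SAP. Study Design and Participants gives the allocation as "22 patients in the Mirror Therapy (MT) group and 21 patients in the Sham Therapy (SHA) group" and then the losses by arm.

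- **MT:** "In the MT group, 4 participants were excluded due to irregular attendance (<75% session compliance"). The same sentence adds "2 participant withdrew their informed consent, and 1 were hospitalized for unrelated medical conditions requiring inpatient treatment".
- **Sham:** "In the SHA group, 4 participants failed to adhere to the intervention frequency, and 2 were excluded because they received additional pain management therapies".

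The 15 participants left in each arm form the analysed set. The exclusion criteria in the same section do not mention pain treatment. The nearest item is "Concurrent participation in other experimental rehabilitation or pharmacological trials", which concerns other trials and not ordinary care during follow-up. Statistical Analysis defines no analysis set, no attendance cut-off and no rule on concomitant treatment. Under Intervention Protocol, the sham description states: "The frequency, duration, and total number of sessions matched those of the experimental group". Attendance is said to have been tracked weekly, with no distinction between arms.

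**The concern.** Any set built by removing people after randomisation, even a deliberate per-protocol set, needs one rule applied identically to both arms. Here the reader cannot tell whether that happened, for two reasons.

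First, the adherence reasons are expressed in different terms. MT has a share of sessions with a cut-off; sham has a reference to frequency with none. The two measures can sort the same attendance record differently.

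Second, added pain treatment is a reason for removal in one arm only. It happens after allocation and may reflect how a participant is doing. Dropping people because of it selects the sham set on something that may be tied to the outcome. The text does not say whether MT participants were checked for it.

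At stake is whether the six-month difference reflects mirror therapy alone or also who was allowed to remain. The statement that sessions were matched describes what was prescribed; it does not show that sessions attended in the two analysed sets were alike.

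**Working it through.** **Inputs.** Randomised: MT 22, sham 21. MT losses: 4 attendance, 2 consent withdrawal, 1 hospitalisation. Sham losses: 4 adherence, 2 pain treatment. Prescribed: 60 sessions, three per week, starting two weeks after injection; follow-up ends six months after injection. Planned effect size d = 0.62 (Statistical Analysis).

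**1. Reproduce the flow.** MT: 22 − 4 − 2 − 1 = 15. Sham: 21 − 4 − 2 = 15. The stated 15 per arm is correct. Total losses are 7/22 (31.8%) vs 6/21 (28.6%), or 13/43 (30.2%) overall.

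**2. Compare removals by reason.**

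| Reason | MT | Sham | Fisher p |
|---|---|---|---|
| Adherence | 4/22 (18.2%) | 4/21 (19.0%) | – |
| Pain treatment | 0/22 | 2/21 (9.5%) | 0.23 |
| Both together | 4/22 (18.2%) | 6/21 (28.6%) | 0.49 |
| All losses | 7/22 (31.8%) | 6/21 (28.6%) | 1.00 |

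For pain treatment, the chance that both cases fall in sham is (21 × 20/2)/(43 × 42/2) = 210/903 = 0.23. Both falling in MT has the larger probability 231/903, so the two-sided p is also 0.23. Counts this small cannot show a difference between arms, or rule one out.

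**3. Do the two adherence phrases measure the same thing?** The MT cut is 0.75 × 60 = 45 sessions. Six months less two weeks leaves about 24 weeks, and 60/24 = 2.5 sessions per week. A participant who spread all 60 sessions over that window would meet the MT cut in full yet fall below three per week. The phrases are therefore not interchangeable if taken literally.

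**4. Possible bias from the two pain-treatment removals.** Of 21 sham participants, 21 − 4 = 17 passed the adherence reason, and 2 of those 17 were then dropped. Assume a normally distributed outcome in SD units.

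- *Extreme case:* the two dropped are exactly the two worst of 17. Their expected values are about −1.79 and −1.32, so the mean of the other 15 moves by (1.79 + 1.32)/15 = 3.11/15 = 0.21 SD (simulation: 0.208). That is 0.208/0.62 = 34% of the planned effect.
- *Correlated case:* removal depends on a marker with correlation ρ to the outcome, and the shift is ρ × 0.208. At ρ = 0.3 it is 0.062 SD (10% of 0.62); at ρ = 0.5 it is 0.104 SD (17%).
- *Cross-check:* if the two differ from those retained by k SD, the shift is (2/17) × k. For k = 0.25, 0.5 and 1.0 this gives 0.03, 0.06 and 0.12 SD.

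If those removed would have done badly, the sham arm looks better and benefit is hidden. If they would have done well, benefit is overstated. The correlations and k values are assumptions; the documents give no outcome data on those removed.

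**The case against.** A reader might infer that the arms were governed by different rules, so that someone attending 80% of sessions would stay in MT but leave sham. The documents do not support this. The flow account lists reasons for loss in the past tense; it does not state rules. A common 75% cut, given once and then paraphrased, with pain treatment disallowed in both arms and no MT case arising, fits the text equally well. Adherence removals of 18.2% and 19.0% give no sign of a stricter sham rule, though they do not prove a common one. The flow illustration is not in the available text and may contain definitions.

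A reader might also infer that the treating therapist, who knew the allocation, decided who was removed. The text says only that therapist supervision was part of adherence monitoring, and that the therapist took no part in outcome evaluation or data analysis. Who decided removals is not stated.

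Three further objections are fair. The MT attendance cut and hospitalisation are equally missing from the listed criteria, so the lack of advance specification is general and not peculiar to sham. MT's three other losses outnumber the two pain-treatment removals. And dropping 13 of 43 after randomisation can bias the comparison even under identical rules, which is the larger issue.

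What survives is narrower. Neither a common rule nor its timing is documented, and the pain-treatment removal conditions on a post-randomisation event whichever reading is correct. Moving to an analysis of all randomised participants would not settle how a compliant set is defined.

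**Conclusion.** The concern holds in limited form. Removal reasons were not specified in advance in these documents and are reported differently by arm, so like selection cannot be verified; it has not been shown to be absent. Removing participants for added pain treatment can bias the between-arm comparison in an unknown direction. A plausible size is 0.06 to 0.10 SD, assuming normality and a correlation of 0.3 to 0.5 between need for pain treatment and outcome. The 0.21 SD figure requires the two removed to be exactly the two most extreme of 17 and should not be read as an estimate. The outcomes are partly ordinal and analysed by rank tests, so these shifts indicate scale only. The adherence part may be small, given the near-equal counts. This should be corrected because the correction is cheap, not because a large bias has been demonstrated.

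**What to change.** - **Pain treatment:** do not use it as a reason for removal from the analysis. Keep those participants in their randomised arm wherever six-month scores exist, and report added pain treatment by arm. If both sham participants have scores, the comparison becomes 15 vs 17.
- **Compliant set:** define it once for both arms as attendance of at least 75% of the 60 mirror or sham sessions (45 or more), taken from the existing attendance records. Someone masked to arm and outcome should apply it. The independent researcher who implemented the randomisation may not meet that condition. Report sessions attended by arm.
- **Order of analyses:** make the compliant set secondary to an analysis of all randomised participants with available data: at most 22 vs 21, or 20 vs 21 if data from the two consent withdrawals cannot be used.
- **Disclosure:** state which attendance and concomitant-treatment rules were applied in each arm, when they were set and who applied them. If one common rule was used, a sentence saying so settles the adherence part.

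The cost is a re-reading of records already kept, a re-run of the analysis and revised text. The arms may no longer be 15 and 15. Completed six-month assessment is documented only for the 30 analysed, so some scores may not have been collected and cannot be restored.

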- **Control Group (Group II, n=15):** Received a sham intervention alongside conventional rehabilitation. In this group, a transparent glass panel was used in place of a mirror, and patients were instructed to observe the reflection of their paretic extremity, thereby eliminating the visual illusion effect central to mirror therapy.

A single-blind study design was implemented to minimize bias. Neither the participants nor the outcome assessors were aware of group assignments. Both the mirror therapy and sham interventions were administered by a licensed physical therapist experienced in neurorehabilitation, who was not involved in data analysis or outcome evaluation.

Evaluation Criteria

Treatment efficacy was assessed at two time points: baseline (prior to BTX-A injection) and six months post-injection. The following standardized clinical instruments were employed to evaluate motor function, spasticity, and muscle strength:

Motor Function: Assessed using the Brunnstrom Recovery Stages, with separate scoring for the hand and upper extremity. This scale provides a stage-based evaluation of motor recovery following stroke, ranging from flaccidity (Stage I) to near-normal movement patterns (Stage VI).

Spasticity: Evaluated using the Modified Ashworth Scale (MAS), which quantifies resistance during passive soft-tissue stretching. The MAS scores range from 0 (no increase in muscle tone) to 4 (rigid in flexion or extension), offering a reliable measure of spasticity severity.

Overall Motor Performance: Measured with the Fugl-Meyer Assessment for Upper Extremity (FMA-UE), a validated and widely used tool that evaluates motor function, coordination, and

reflexes in the paretic arm. Scores range from 0 to 66, with lower scores indicating more severe impairment.

Muscle Strength: Quantified using a handheld dynamometer (Jamar® or equivalent) for both the paretic and non-paretic upper extremities. Grip strength (in kilograms) was recorded as the maximum value of three consecutive trials, with standardized positioning to ensure consistency.

All assessments were conducted by a trained physiotherapist ([name]) blinded to group allocation. Standardized testing protocols were followed across all time points to ensure inter-session reliability.

Intervention Protocol

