All participants initiated their rehabilitation and mirror/sham therapy sessions two weeks after the BTX-A injection, coinciding with the onset of the toxin's maximal clinical effect. Adherence to the intervention protocol was strictly monitored throughout the study period.

Statistical Analysis

All statistical analyses were performed using IBM SPSS Statistics for Windows, Version 22.0 (IBM Corp., Armonk, NY, USA). The normality of continuous variables was assessed using the Shapiro-Wilk test. As the data were not normally distributed, non-parametric tests were employed for all comparisons. Continuous variables were expressed as mean \pm standard deviation (SD), and categorical variables were presented as frequencies and percentages. Between-group comparisons at baseline and post-treatment were conducted using the Mann-Whitney U test for continuous variables and the Chi-square test for categorical variables. To evaluate within-group changes from pre- to post-treatment, the Wilcoxon signed-rank test was used. In addition, Spearman's rank-order correlation coefficient (ρ) was calculated to assess the relationships between changes in motor function, spasticity, and muscle strength. A two-tailed p-value < 0.05 was considered statistically significant for all analyses. No corrections for multiple comparisons were applied, as the primary outcomes were pre-specified.

A priori sample size estimation was performed using G*Power software (Version 3.1), assuming a two-tailed test with an effect size of $d = 0.62$, $\alpha = 0.05$, and power $(1-\beta) = 0.80$. A minimum total sample size of 28 participants (13 in one group and 15 in the other) was deemed sufficient to detect statistically meaningful between-group differences.

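### Enrolment to February 2025, six months of follow-up for each participant, and evaluations complete by March 2025 cannot all be true as written

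*Combined protocol and SAP*

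**What the plan says.** The participant-flow paragraphs under Study Design and Participants make three statements about dates.

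- Enrolment: "A total of 43 participants were initially enrolled between May 2024 and February 2025".
- Follow-up and completion, in one sentence: "The follow-up period for each participant lasted six months after BTX-A injection, and all post-treatment evaluations were completed by March 2025".

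The same paragraphs give the order of events ("Following baseline evaluations and BTX-A injections, participants were randomly allocated into two groups") and say of the conduct of the trial: "The study was conducted according to the approved protocol and completed as planned without early termination". The 15 participants analysed in each group are described as having "completed the full 6-month intervention and follow-up assessments and were included in the final statistical analysis".

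Evaluation Criteria fixes the assessments: "Treatment efficacy was assessed at two time points: baseline (prior to BTX-A injection) and six months post-injection". Intervention Protocol says that "all participants in both groups underwent a standardized conventional upper extremity rehabilitation program for a duration of 6 months" and gives 60 mirror or sham sessions at three per week. On the start of sessions, the document says: "All participants initiated their rehabilitation and mirror/sham therapy sessions two weeks after the BTX-A injection".

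**The concern.** A trial that is still enrolling in February 2025 cannot have six-month outcomes on its last entrants by the end of March 2025. The document mentions no interim visit, no shortened follow-up for late entrants and no early stop.

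The endpoint itself depends on this. The six-month visit is the only assessment after baseline, so every post-treatment Mann-Whitney comparison, every within-group Wilcoxon test and every correlation of changes rests on it. There are two possibilities.

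- **A calendar date is wrong** (close of enrolment or completion of evaluations). Possibly no analysed outcome is affected, and a text correction is enough.
- **Both calendar dates are right.** Some outcomes may then have been measured before six months, unless everyone injected after 30 September 2024 is among the 13 participants not analysed. Early outcomes could not be reported as six-month effects.

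**Working it through.** **Inputs**

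- Enrolment from May 2024 to February 2025, 43 participants (Study Design and Participants). Taken as 1 May 2024 to 28 February 2025.
- Follow-up of six months after injection, all evaluations complete by March 2025 (same section). Taken as 31 March 2025, the most generous reading.
- Injection before allocation (same section). Sessions start two weeks after injection (before Statistical Analysis).
- 60 sessions at three per week (Intervention Protocol).
- 30 analysed, so 43 − 30 = 13 not analysed.

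**Can the stated completion date be reproduced?** No.

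1. Forwards: 1 February 2025 + 6 months = 1 August 2025, which is 123 days after 31 March 2025. For 28 February the date is 28 August 2025. Injection later than enrolment only lengthens the gap.
2. Backwards: 31 March 2025 − 6 months = 30 September 2024, the last workable injection date.
3. Share of the enrolment window after that date: the window is 304 days; October to February is 31 + 30 + 31 + 31 + 28 = 151 days; 151 / 304 = 49.7%.

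**Do other readings remove the conflict?**

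- *Enrolled means allocated.* If allocation precedes the first mirror or sham session, it trails injection by at most 14 days. The last workable allocation date is 30 September + 14 days = 14 October 2024, and 137 / 304 = 45.1% of the window falls later. Allocation on 1 February 2025 means injection no earlier than 18 January, so six months falls on 18 July 2025, 109 days late.
- *The session course marks the end.* 60 / 3 = 20 weeks; with the two-week delay, 22 weeks. From 1 February 2025 this ends on 5 July 2025. Only 58 days separate 1 February from 31 March; less 14 days, 44 / 7 × 3 = 18.9, so about 18 full sessions of 60 would fit.

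**Relaxing one statement at a time**

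| Kept | Consequence |
|---|---|
| Enrolment to February 2025 and six months | Last evaluation falls between 1 and 28 August 2025 |
| Six months and completion by 31 March 2025 | Last injection no later than 30 September 2024 |
| Enrolment to February 2025 and completion by 31 March 2025 | February entrants have at most 31 to 58 days of follow-up |

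**How many of the 30 could be affected if both calendar dates are right?** If L of the 43 entered too late, the number among the 30 lies between max(0, L − 13) and min(30, L). L is not given, so without further assumptions the range is 0 to 30.

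For illustration only, assume even accrual, which the document does not state. Then L = 43 × 0.497 = 21.4, about 21. The minimum among the 30 is 21 − 13 = 8. The maximum is 21, if all 13 not analysed entered early (22 − 13 = 9 early, and 9 + 21 = 30). On the allocation reading, L = 43 × 0.451 = 19.4, about 19, with a range of 6 to 19. These lower ends are not floors once the even-accrual assumption is dropped.

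**The case against.** The best counter-argument is that the six-month statement was meant for completers. The same paragraphs report withdrawals and exclusions, so not all 43 can have been followed to the end. If everyone injected after 30 September 2024 is among the 13 not analysed, all 30 analysed participants could have true six-month assessments by March 2025.

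This is possible, but the document does not say it. It needs at most 13 of the 43 to have been injected after that date, although enrolment ran for five further months, and every one of them to have been excluded. The reasons given are poor attendance or adherence, withdrawn consent, hospitalisation and additional pain treatment; none is insufficient follow-up time. The sponsor would have to show this from records, and the sentence about each participant would still need rewording.

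Three further points deserve weight. The counts under even accrual rest on an unstated assumption and serve only as illustration. The document gives no visit window, so a re-analysis that dropped anyone assessed a few days early would be too strict; a tolerance has to be stated. And a mistyped month is a simple explanation that would leave the results untouched, so one can argue for a lower rating. The correction is still required, because the only post-baseline time point cannot be verified from the dates given.

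**Conclusion.** The concern holds. The enrolment period, six months of follow-up for each participant and completion by March 2025 conflict as written, by 123 days for the earliest February 2025 entrant (109 days if enrolment means allocation). About half of the enrolment window, 49.7%, lies after the last workable injection date. This rests only on calendar arithmetic and the most generous reading of the completion date, and confidence in it is high.

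Confidence is low on how many of the 30 analysed outcomes are affected, if any. It may be none. The document does not show which statement is wrong, and it gives no evidence that the two groups are affected differently. Correction is essential in order to reconcile the dates; early assessment is not presumed.

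**What to change.** Check the injection date and the final-assessment date of all 43 participants against source records. Then correct whichever statement is wrong: the close of enrolment, the completion of evaluations, or six months of follow-up for each participant. If the last of these was meant for completers only, say so and give the range of their injection dates.

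Only if an analysed participant was assessed before six months:

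- state the tolerance used to define a six-month assessment;
- report actual follow-up times, and the number with a true six-month assessment, by group;
- do not call the endpoint six-month for the others;
- repeat the planned Mann-Whitney and Wilcoxon tests in those with a true six-month assessment.

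The cost is a date check on 43 records and a wording correction. If early assessments are found, add a re-run of the planned tests in a smaller set, with lower precision and a weaker six-month claim.
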